
FEV₁ = forced expiratory volume in 1 second; pred = predicted * Determined from participant recall, based on the 2-week interval directly preceding the study visit. **Predicted references are provided in the Protocol ICAC-28 MOP. *** Defined as a prescription of a course of systemic steroids by a clinician or initiation of a course of systemic steroids by a participant to prevent a serious asthma outcome. If a participant initiates and completes a course of systemic steroids without clinician involvement, this course will be counted only if it meets the following dosage: the course for prednisone, prednisolone, or methylprednisolone will be 2 mg/kg/day as a single daily dose for 4 days with a maximum dose of 60 mg per day. The course for dexamethasone will be 0.3 to 0.6 mg/kg/day as a single daily dose for 2 days with a maximum dose of 16 mg per day. If a corticosteroid burst for the treatment of an asthma exacerbation is prescribed by a non-ICAC clinician, it will be counted regardless of dose.
				

Next, the study clinician will determine the current level of controller therapy that the participant is using. Table 7.1.1.1b shows the asthma regimens that will be used during the treatment phase of Protocol ICAC-28 CRITICAL. If the participant is currently on one of the therapies below, then the step level of that therapy will be noted. Otherwise, the study clinician must refer to the Protocol ICAC-28 MOP for equivalency tables for other asthma therapies. From the information in the Protocol ICAC-28 MOP, the study clinician will determine the corresponding step level of therapy that the participant is currently using. For example, if the participant is currently taking Flovent® Diskus® 250 mcg twice per day (bid), then he/she is receiving Step 3 therapy.

Table 7.1.1.1b Asthma Regimen by Step Level of Therapy

Step	Medication Equivalent*
0	No controller medication; albuterol or levalbuterol prn
1	fluticasone 50 mcg bid
2	fluticasone 100 mcg bid
3	fluticasone 250 mcg bid
4	fluticasone 250 mcg bid plus LABA
5	fluticasone 500 mcg bid plus LABA

bid = twice per day; LABA = long-acting beta agonist

*Equivalent medication covered by participant’s insurance formulary – see Protocol ICAC-28 MOP.

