7.1.1.2 Study Period Treatment Regimen

At Randomization and every 2 months during treatment, an asthma Evaluation and Management (E&M) process will occur where participants’ asthma medication regimen will be adjusted based on symptoms, albuterol/levalbuterol use, FEV₁, recent exacerbations, and their current level of therapy.

Participants may be stepped down from controller medications if their control level is equal to 1 at Screening, Asthma Control Visits, and at some E&M visits while the participant is in maintenance (see Appendix B: Study Restrictions Due to COVID-19). Participants may not be stepped down from controller

medications at Randomization or during Dose Escalation. Participants may be stepped up as per the protocol algorithm at any visit where indicated.

Participants will undergo pre-bronchodilator spirometry and an assessment of symptoms, rescue bronchodilator usage, recent exacerbations and medication adherence. Bronchodilator use as a preventive measure prior to exercise will not count toward the assessment of rescue bronchodilator use. Based on these data, a study clinician will determine the participant’s current control level from Table 7.1.1.2a below. The control levels originated from the published national guidelines, Guidelines for the Diagnosis and Management of Asthma.²⁸

For all participants, the highest control level for days with symptoms or albuterol/levalbuterol use, nights with symptoms or albuterol/levalbuterol use, percent personal best FEV₁, and exacerbation history will be determined by the study clinician. The day and night symptoms, albuterol/levalbuterol use, adherence to prescribed asthma controller medications by self-report, and exacerbation history will be determined from questionnaires. The FEV₁ personal best is defined in the Protocol ICAC-28 MOP. If the quality of the spirometry maneuver at the current visit is unacceptable according to the technician’s judgment, FEV₁ in Table 7.1.1.2a will not be used, and the control level will be based on day and night symptoms, albuterol/levalbuterol use, and exacerbation history. For example, if a participant has 0 days with symptoms (control level 1), 4 nights with symptoms (control level 3), FEV₁ at 85% of personal best (control level 1), and 1 exacerbation (control level 2), then the participant’s overall control level is 3 because that is the maximum value of control levels 1, 3, 1, and 2.

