Table 7.1.1.2b Treatment Adjustment Based on Control Levels and Adherence

Control Level	Treatment Algorithm for Participants with Unacceptable Adherence	Treatment Algorithm for Participants with Acceptable Adherence
1	If on Step 0, maintain at Step 0 If on Steps 1-5, decrease controller regimen by 1 step ** Do not decrease controller regimen at Randomization or during Dose Escalation	If on Step 0, maintain at Step 0 If on Steps 1-5, decrease controller regimen by 1 step ** Do not decrease controller regimen at Randomization or during Dose Escalation
2	Continue same controller regimen or place on Step 2 therapy, whichever is higher	Increase controller regimen by 1 step, or continue Step 5 therapy if already on Step 5
3	Continue same controller regimen or place on Step 2 therapy, whichever is higher	No systemic steroids since the Last Medication Management visit* If on Steps 0-4 increase controller regimen by 1 step If on Step 5 continue Step 5 or treat with Step 5 and a 4 day burst of prednisone or equivalent; ≥1 course(s) of systemic steroids since the last E&M visit* If on steps 0-3 increase controller regimen by 2 steps If on treatment Step 4 increase controller regimen to Step 5 or treat with Step 5 and a 4 day burst of prednisone or equivalent If on treatment Step 5 continue Step 5 or treat with Step 5 and a 4 day burst of prednisone or equivalent
4	Continue same controller regimen or place on Step 3 therapy, whichever is higher OR Treat with 4-day prednisone burst and continue same controller regimen or place on Step 3 therapy, whichever is higher	If on Steps 0-3 increase controller regimen by 2 steps If on Step 4, increase to Step 5 or treat with Step 5 and a 4-day prednisone burst or equivalent If already on Step 5, continue on Step 5 or treat with Step 5 and a 4-day burst of prednisone or equivalent

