7.1.2 Other permitted concomitant medications

During the study, after the initial skin testing, rhinitis and asthma medications will be permitted along with other maintenance medications, aside from those excluded in Section 4.3, Exclusion Criteria. Short courses of oral corticosteroids or doses of greater than 500 mcg of fluticasone per day or the equivalent of another inhaled corticosteroid may be used short-term (not to exceed 6 months) to control an asthma exacerbation.

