7.3 Prohibited Medications

1. A regular dose of greater than 500 mcg of fluticasone per day or the equivalent of another inhaled corticosteroid for a duration of ≥ 6 months
2. Allergen immunotherapy (SLIT or SCIT)
3. Biologic therapies (e.g., anti-IgE, anti-IL-4, anti-IL-5)
4. Tricyclic antidepressants
5. Beta-adrenergic blocker drugs (both oral and topical)
6. Any investigational drug

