Dose escalation will continue according to the schedule unless there are lapses in dosing or reactions occur. Dosing modifications as a result of reaction or lapse in dosing during dose escalation are detailed in the MOP for Protocol ICAC-28.

Participants who are unable to reach the minimum maintenance dose (the highest volume of the 1:10 concentration; Dose 20 in Table 8.6.1) by 40 weeks following the start of dose escalation will be unable to proceed to the maintenance period and will have their study therapy stopped (see Section 11.2.1; see Appendix B Study Restrictions Due to COVID-19).

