11.2 Participant Stopping Rules and Withdrawal Criteria

11.2.1 Discontinuation of Study Therapy

Study therapy may be prematurely discontinued for any participant for any of the following reasons:

1. SAE related to investigational agent.
2. Systemic reaction grade 3 or 4 (see Table 12.3.1.1c, WAO Systemic Reaction Grading System).
3. Failure to reach the minimum maintenance dose in a forty-week period (See Appendix B: Study Restrictions Due to COVID-19).
4. Development of any serious medical illness whose natural history, sequela, or treatment would be worsened or impaired by continuation in the protocol.
5. The participant has a need to start immunotherapy or any chronic immunosuppressive medications.
6. The participant has a need for a dose of greater than 500 mcg of fluticasone per day, or the equivalent of another inhaled corticosteroid, to maintain asthma control for greater than 6 months.

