Appendix B: Study Restrictions Due to COVID-19

In the event of institutional or ICAC-wide restrictions on certain types of procedures or certain classes of research, some study activities will be suspended. This includes certain visits and specific inhalation and nasal procedures, such as:

- In-person study visits, including injection visits
- Spirometry
- Nasal Allergen Challenges
- Nasal sampling, including nasal lavages
- Peak Expiratory Flow

When all in-person study activities are suspended, study staff will continue to make contact with study participants over the phone and clinicians will continue to manage the participants' asthma remotely. Prescriptions for asthma management medications can be sent to local pharmacies and additional prednisone, if needed, can be mailed to the participant. Should re-consenting be necessary, the consent process will occur remotely.

Participants whose immunotherapy regimen was halted as a result of study activity restrictions will be asked to resume therapy once the site is able to administer injections. The initial restart dose for these participants will be dictated by the dose modification rules in the Protocol ICAC-28 MOP. Re-escalation of immunotherapy will follow the rules referenced in Section 8.6 and in the Protocol ICAC-28 MOP, taking into account each participant's total time off therapy and history of reactions. The 40-week requirement for reaching maintenance will be reset for participants whose immunotherapy was interrupted by the COVID-19 pandemic.

While participants may typically be stepped down from controller medications during the maintenance phase, participants in this phase who had their therapy level modified as a result of the COVID-19 pandemic will not be stepped down in MEDS treatment level until they have successfully re-escalated to their original maintenance dose.

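### The ban on stepping controllers down during dose escalation can hold a controlled child on Step 5 (1000 mcg/day) beyond the six months at which Protocol 7.3 makes that dose prohibited

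*Protocol*

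**What the plan says.** **The step-down rule.** For control level 1, Table 7.1.1.2b carries the note "Do not decrease controller regimen at Randomization or during Dose Escalation". The text of Protocol 7.1.1.2 repeats this ban on decreases and, directly after it, leaves increases open: "medications at Randomization or during Dose Escalation. Participants may be stepped up as per the protocol algorithm at any visit where indicated". After escalation, that section allows a decrease only at some of the maintenance Evaluation and Management (E&M) visits, which fall every two months.

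**The dose.** Table 7.1.1.1b defines Step 5 as "fluticasone 500 mcg bid plus LABA". An adherent child on Step 4 moves to Step 5 at control level 2, 3 or 4. A child on Step 3 can rise two steps at level 4, or at level 3 after a course of systemic steroids.

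**The limits.** Section 7.3 prohibits "A regular dose of greater than 500 mcg of fluticasone per day" (or the equivalent) once it has lasted six months or longer. Section 7.1.2 says such doses "may be used short-term (not to exceed 6 months) to control an asthma exacerbation". Section 11.2.1 item 6 lists as a possible reason to stop study therapy: "The participant has a need for a dose of greater than 500 mcg of fluticasone per day", where that need lasts more than six months.

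**The duration of escalation.** Under section 8.6.1, the minimum maintenance dose must be reached "by 40 weeks following the start of dose escalation". Appendix A gives 16 to 26 weeks as normal. Appendix B resets the 40-week clock for children whose injections were interrupted by COVID-19. It adds that affected maintenance participants "will not be stepped down in MEDS treatment level until they have successfully re-escalated to their original maintenance dose".

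**The concern.** Two rules can apply to the same child on the same day and require opposite things. The table obliges the clinician to leave a controlled child on Step 5 for as long as escalation lasts, while section 7.3 makes that same dose a prohibited medication once six months have passed. The prohibition depends on dose and duration, so good asthma control does not lift it. I found no passage that exempts a child held by the ban or lets the clinician override it during escalation, and section 15.1.1 permits no deviations.

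Two things are at stake. One is how long a child who is no longer symptomatic stays on the highest inhaled steroid step for an administrative reason. The other is the meaning of the deviation record: a prohibited-medication deviation produced by following the algorithm would look the same as one that reflects poorly controlled asthma.

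**Working it through.** **Inputs**
- Doses: Table 7.1.1.1b.
- Escalation: Table 8.6.1, section 8.6.1 and Appendix A.
- E&M visits every two months: section 7.1.1.2.
- Limit: section 7.3.
- One month is taken as 365.25/12 = 30.44 days.

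**The plan's own figure first.** Doses 1–20 at two a week take 20/2 = 10 weeks, and Doses 21–26 at one a week take 6 weeks, total 16 weeks. All 26 doses at one a week take 26 weeks. Both ends of the 16–26 week range in Appendix A are reproduced.

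**Which step crosses the limit**
- Steps 3 and 4: 2 × 250 = 500 mcg/day, not above 500.
- Step 5: 2 × 500 = 1000 mcg/day, above 500.

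So Step 5 is the only step above the limit, and one permitted step-down would end the exposure.

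**Ban against limit**
- Longest escalation: 40 × 7 / 30.44 = 9.2 months.
- Limit: 6 × 30.44 / 7 = 26.1 weeks.
- The ban can outlast the limit by up to 40 − 26.1 = 13.9 weeks.

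**Child moved to Step 5 at the month-2 E&M visit** (2 × 30.44 / 7 = week 8.7) and controlled from then on:

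| Escalation ends | Held to end of escalation | Held to next scheduled E&M visit |
|---|---|---|
| Week 16 | (16 − 8.7) × 7 / 30.44 = 1.7 months | Month 4: 2 months |
| Week 26 | (26 − 8.7) × 7 / 30.44 = 4.0 months | Month 6: 4 months |
| Week 30 | (30 − 8.7) × 7 / 30.44 = 4.9 months | Month 8: 6 months |
| Week 35 | (35 − 8.7) × 7 / 30.44 = 6.05 months | Month 10: 8 months |
| Week 40 | (40 − 8.7) × 7 / 30.44 = 7.2 months | Month 10: 8 months |

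The right-hand column matters because a decrease is tied to particular visits. A child still escalating at the month-6 visit (week 26.1) cannot be stepped down there. The next scheduled opportunity is month 8, and 8 − 2 = 6 months already meets the threshold in section 7.3. Counting only to the end of escalation, the threshold is passed once escalation exceeds 8.7 + 26.1 = 34.8 weeks.

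**Child moved to Step 5 at month 4, 40-week escalation.** 5.2 months to week 40, and 10 − 4 = 6 months to the month-10 visit.

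**The three six-month wordings.** At exactly six months, the dose is still within section 7.1.2 (not to exceed), already prohibited by section 7.3 (at or beyond), and not yet within section 11.2.1 (longer than).

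**The case against.** The strongest reply is that this is an edge case. It needs an early move to Step 5, return to control level 1, and a slow escalation. Within the 16–26 weeks that Appendix A calls normal, a month-2 step-up is held four months at most and nothing is breached. That stands, and it limits the point. It does not remove it: 40 weeks is expressly allowed, and Appendix B can lengthen the hold. SAP 7.3 even gives 26 weeks as the minimum, which leaves almost no room before the month-6 visit.

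It can also be said that section 7.1.2 covers other concomitant medications, whereas step care is protocol-mandated under 7.1.1, so 7.1.2 need not govern the algorithm's own steps. That is fair. The conflict therefore rests on section 7.3, and 7.1.2 matters only for its differing wording.

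A reader might infer three stronger things that the documents do not support:
- **That such a child must lose study therapy.** Section 11.2.1 item 6 requires a need for the dose, and the section says therapy may be discontinued. A controlled child held only by the ban does not clearly meet it.
- **That the table, run at Randomization, makes an eligible child ineligible under exclusion 4a.** That criterion concerns children who require more than 500 mcg/day, and section 8.5 places the eligibility review before the medication adjustment.
- **That the hold is longer on active treatment and unbalances the arms.** Reactions can delay escalation, but section 8.6.1 also allows delay for other concerns, and no delay or reaction rates by arm are given.

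**Conclusion.** The conflict between Protocol 7.1.1.2 with Table 7.1.1.2b and section 7.3 is real and can be reached by following the protocol exactly. For a month-2 step-up, the hold on 1000 mcg/day is 7.2 months to the end of a 40-week escalation and 8 months to the month-10 visit. It reaches six months for any child still escalating at the month-6 visit.

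This assumes that E&M visits fall on schedule, that the child stays at control level 1 after the step-up, and that step-down waits for a scheduled maintenance E&M visit. If a decrease were allowed as soon as escalation ended, the 34.8-week threshold would apply instead.

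How many children are affected cannot be derived from the documents. The statistical reach is small: only exploratory endpoints, treatment step and CASI at months 10 and 12, could be touched. A child who finishes escalation at week 40 could come down by at most one step, at month 10, before the month-12 assessment. None of the SAP analysis samples is defined by prohibited medication, so the breach itself removes nobody from the primary analysis. The point merits correction because it concerns children's steroid exposure and the integrity of the deviation count.

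**What to change.** **Protocol.** The sponsor should reconcile 7.1.1.2 and Table 7.1.1.2b with section 7.3 and Appendix B, so that it is clear which instruction applies when a child on Step 5 is still escalating at six months. The six-month wordings in 7.1.2, 7.3 and 11.2.1 item 6 should be aligned. Which rule governs is for the sponsor's clinicians. The reconciliation should not be written as a guarantee that no child managed by the table can ever become ineligible or meet a discontinuation criterion, because that would settle a clinical question in advance.

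**SAP.** Add to section 7.1 a listing, by arm, of children held at Step 5 for six months or more under the no-decrease rule. It should show the date of step-up, the control level at each later E&M visit, and the date when a step-down first became permitted. Classify prohibited-medication deviations as created by the algorithm or as reflecting clinical need.

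**Cost.** A short protocol clarification with a notice to sites, and one listing from data already collected. The SAP (version 1.0, dated 2022-06-09) describes randomization in the past tense, so escalation may be largely or wholly complete. If it is complete, only the listing and the deviation classification still apply.

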7.1.1.3 Final Study Visit

At the Final Study Visit (12-month Visit), the final treatment regimen prescribed will be based on the protocol-based medications management algorithm or the discretion of the study clinician who examines the participant. The study clinician will base the treatment on factors such as symptoms, albuterol use, spirometry, adherence, and the participant's current level of therapy. The participant's care will then be transferred back to their primary care provider (PCP) and/or asthma specialist.

7.1.1.4 Asthma Action Plan

Clinical research staff will provide a written Asthma Action Plan consistent with NAEPP guidelines for the participant at all E&M visits. This plan describes a Green, Yellow, and Red Zone for the participant based on his/her symptoms. In the Green Zone, the participant has no symptoms of an asthma episode and is directed to use his/her usual asthma medications. In the Yellow Zone, the participant is experiencing asthma, allergy, or cold symptoms, and is directed to increase rescue medication use until the symptoms have been resolved. In the Red Zone, the participant is having persistent symptoms that cannot be controlled. The participant is instructed to contact a study clinician or go to the emergency department (ED) if unable to contact a study clinician.

7.1.1.5 Asthma Education

As part of the meeting at E&M visits with a clinical research staff member for asthma education, participants will be educated on topics related to asthma. These topics include background on asthma as a disease, use of the Asthma Action Plan (see Section 7.1.1.4), adherence to medications, using medications at school (when applicable), and allergen and irritant avoidance. Handouts will be provided and the education content will be tailored to each participant. For example, the allergen avoidance education will be based on the participant's aeroallergen skin test/serum IgE results. The participant will receive education about the allergens to which he/she is sensitive. The information contained in the handouts will be based on the EPR-3: Guidelines for the Diagnosis and Management of Asthma and on experience from previous ICAC clinical trials.

7.1.2 Other permitted concomitant medications

During the study, after the initial skin testing, rhinitis and asthma medications will be permitted along with other maintenance medications, aside from those excluded in Section 4.3, Exclusion Criteria. Short courses of oral corticosteroids or doses of greater than 500 mcg of fluticasone per day or the equivalent of another inhaled corticosteroid may be used short-term (not to exceed 6 months) to control an asthma exacerbation.

7.2 Prophylactic Medications

Pre-treatment with antihistamines can be used before immunotherapy injection at the study clinician's discretion.

7.3 Prohibited Medications

1. A regular dose of greater than 500 mcg of fluticasone per day or the equivalent of another inhaled corticosteroid for a duration of ≥ 6 months
2. Allergen immunotherapy (SLIT or SCIT)
3. Biologic therapies (e.g., anti-IgE, anti-IL-4, anti-IL-5)
4. Tricyclic antidepressants
5. Beta-adrenergic blocker drugs (both oral and topical)
6. Any investigational drug

7.4 Rescue Medications

Participants may use antihistamines as needed for large local reactions to the injections.

Participants may use antihistamines and/or a nasal steroid as needed for persistent nasal and/or ocular symptoms following the NAC. If at any time during the NAC a participant experiences asthma symptoms or anaphylaxis, treatment with inhaled short-acting bronchodilators, corticosteroids and epinephrine will be immediately available to treat the reaction. Participants will be instructed to bring an albuterol inhaler to any visit in which a NAC will be performed and carry it with them for the first 24 hours after the NAC. Participants who do not bring an albuterol inhaler to a NAC visit will be provided one.

